2.8.2.2.6. Plasma Therapy

Plasma therapy will be analyzed as follows:

- The number and percent of patients who do not receive any plasma therapy (plasma exchange or plasma infusion) during study will be summarized separately for patients who have or have not used plasma therapy before Day 1 by dose and disease for the safety analysis population.
- The number of plasma infusions received, and the number of plasma exchanges received post baseline will be summarized by dose and disease for the safety analysis population.

[REDACTED]

2.8.4. Safety Analyses

All safety analyses will be descriptive in nature Section 3.4.

2.8.5. Timing of Planned Analyses

The coronavirus associated lockdown situation in various countries has created uncertainty in the ability to collect all follow-up data and resolve all queries on a few patients enrolled in the study. When adequate data on the primary and secondary endpoints is available, the database will be

locked for interim analyses and creation of an interim CSR to enable regulatory submission for drug approval. Efforts will continue to collect additional follow-up data and resolve any outstanding queries.

3. STATISTICAL SUMMARIES

3.1. General Conventions

All data summaries will be descriptive in nature. Summary statistics for continuous variables will include number of patients, mean, median, standard deviation, minimum, and maximum. For categorical variables, frequencies and percentages will be provided. All confidence intervals will be constructed at the two-sided 95% confidence level.

Efficacy analyses will be focused on the HSCT-TMA patients. Atypical hemolytic uremic syndrome and TTP patients will be summarized separately by OMS721 dose.

All statistical analyses will be performed using SAS version 9.4 or later (SAS Institute Inc., Cary, NC).

3.2. Patient Disposition and Treatment

3.2.1. Patient Disposition

The number of patients treated, completing the study, and terminated from the study early will be summarized by dose and disease for the safety analysis population. The reason for early termination from the study will be summarized. A list of patients failing any eligibility criteria will be provided.

In addition, the eligibility criteria for the TMA diagnosis in HSCT-TMA patients will be summarized.

3.2.2. Study Treatment Compliance and Extent of Exposure

3.2.2.1. Study Treatment Compliance

No specific analyses for treatment compliance are planned for this study. A listing of any patients not completing treatment for any reason will be provided.

3.2.2.2. Extent of Exposure

Scheduled drug administrations will be summarized with the total dose volume (mL) received, the total intended dose volume (mL), the number of doses received and the duration of treatment will be summarized by dose and disease. Intended dose volume for doses in mg/kg at each dose administration is calculated as:

$$\text{Intended dose in mg/kg} \times [\text{minimum of Weight (kg) and 100}] \div 100.$$

As of OMS721-TMA-001 Protocol Amendment [REDACTED], the intended dose is 370 mg weekly and the drug concentration is 185 mg/mL. Therefore, the intended dose volume for each dose administration is $370/185 = 2$ mL.

Relative dose intensity (%), defined as the total dose volume received as a percentage of the total intended dose volume will be summarized by dose and disease. The number of patients whose duration of treatment is ≥ 1 week, ≥ 4 weeks and ≥ 8 weeks may also be summarized.

The number of doses received for the supplemental OMS721 treatments due to plasma therapy will be summarized by dose and disease.

Listing of dosing information will also be provided.

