No use, disclosure, or reproduction outside of Omeros without prior written authorization

enrollment in the study has been completed. Patients completing Stage 2 may be eligible for continued treatment in Stage 3 if they have tolerated OMS721 treatment and derived clinical benefit.

OMS721 is to be used in conjunction with standard of care treatments. Standard of care treatments are not to be delayed or withheld from patients entering this study. These treatments should be initiated according to local standard of care. For example, plasma exchange should not be delayed while waiting for initiation of OMS721 treatment if local standard of care is to administer plasma exchange.

OMS721 will be administered by intravenous (IV) infusion. The cohorts and treatments are provided below.

For patients with HSCT-TMA enrolled under Amendment 10 or earlier versions of this protocol, additional data will be collected. These data will include supplemental data on patient demographics and baseline conditions, donor characteristics, the transplant procedure, concomitant medications, TMA-related laboratory measures, transfusions, transplant complications, and outcomes. These data will be derived from medical records from the time of transplant conditioning through the last available patient contact with the site, or up to 2 years (104 weeks) following the first dose of OMS721, whichever comes first. These data were requested by regulatory authorities because patients who have undergone HSCT typically have complicated post-transplant courses, and these additional data will provide the needed information to draft patient narratives, including the full patient profile, and allow for better understanding of OMS721 response and outcomes.

As of Amendment 11, enrollment in the study has been completed, and the additional data will be collected until a predetermined data cutoff date for those patients who have not reached 2 years after first OMS721 dose.

Cohort (Number)	Stage	Treatment
1 (N = 3)	1	OMS721 Dose 0.675 mg/kg IV weekly x 4
2 (N = 3)	1	OMS721 Dose 2.0 mg/kg IV weekly x 4
3 (N = 3)	1	OMS721 Dose 4.0 mg/kg IV weekly x 4
4 (N = 40 aHUS) As of Amendment 10, Cohort 4 is closed	2	OMS721 Dose 4.0 mg/kg IV weekly x 12
4 (N ≤ 40 aHUS) As of Amendment 10, Cohort 4 is closed	3	OMS721 Dose 4.0 mg/kg IV weekly x 12

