9. STUDY DRUG AND TREATMENT OF PATIENTS

OMS721 is manufactured using current Good Manufacturing Practices for investigational use. OMS721 is a human IgG4 mAb directed against MASP-2. Two formulations are available, the higher concentration drug product (185 mg/mL) and the lower concentration drug product (100 mg/mL), depending on which amendment patients were enrolled under (see Section 9.1.3).

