9.1. OMS721 Drug Product

OMS721 100 mg/mL Injection Solution is a clear, colorless to yellow-brown liquid. It consists of 2 mL OMS721 Drug Substance, formulated in 20 mM sodium acetate, 5% sorbitol, and 0.01% polysorbate 80, pH 5.0 ± 0.8, at a concentration of 100 mg/mL, and supplied in a single-use 5 mL sterile, clear-glass vials. Each vial contains 2 mL of 100 mg/mL Injection Solution. As of Amendment 10 of this protocol, the 100 mg/mL formulation will not be used for newly enrolled patients.

Drug Product, OMS721 185 mg/mL is a clear, colorless to yellow-brown liquid. It contains OMS721 Drug Substance (nominal concentration of 185 mg/mL), formulated at pH 5.8, in citrate (20 mM), arginine (200 mM), and polysorbate 80 (0.01%). The Drug Product is supplied in a single-use type I glass 2 mL vial containing 2 mL of solution.

The OMS721 Drug Product (185 mg/mL) will be further diluted for IV administration in accordance with the preparation instructions described below.

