9.1.3. Study Drug Dose Preparation

Prior to preparation, the study drug should be inspected for any particulate matter or discoloration. If any particulate matter or discoloration is observed, the vial should not be used. As of Amendment 10 of this protocol, only the Drug Product, OMS721 185 mg/mL formulation will be used. The refrigerated vials (Drug Product, OMS721 185 mg/mL) must be used within 4 hours following septum piercing. Do not shake or heat the OMS721. Avoid exposure to direct sunlight.

As of Amendment 10 of this protocol, the dose is changed to a fixed dose of 370 mg.

For dispensing, Drug Product OMS721 185 mg/mL is removed from refrigerated storage and allowed to come to room temperature undisturbed for a minimum of 30 minutes and then used to prepare the appropriate dosing solution.

The appropriate calculated volume of Drug Product, OMS721 185 mg/mL will be withdrawn from the vial using polypropylene syringes for dose preparation.

The measured OMS721 dose will be added to a polyvinyl chloride or polyolefin infusion bag containing a minimum of 50 mL D5W or normal saline for injection solution and mixed by gentle inversion about 10 times. The infusion preparation should not be shaken. The prepared infusion bag should be properly labeled, including the date and time of preparation, and kept at room temperature until ready for administration. The infusion bag should be administered within 4 hours of preparation. If the infusion bag is not used within 4 hours, then it should be discarded and the disposition recorded under drug accountability.

The diluted study drug should be infused intravenously over approximately a 30-minute period.

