9.1.5. Study Drug Accountability

In compliance with the US FDA, European Medicines Agency (EMA), and other applicable regulations, records will be maintained by the Investigator and/or pharmacist designee for OMS721 study Drug Product delivery to the site, the inventory at the site, the use of each vial, and the return of used and unused Drug Product, including dates and quantities. The Investigator and/or pharmacist designee will maintain the investigative site's study drug accountability documentation. The documentation should include the identification of the Drug Product used, Drug Product, OMS721 100 mg/mL Injection Solution or Drug Product, 185 mg/mL. After the study has been completed, a copy of the Investigator/pharmacy drug accountability records will be provided to the Sponsor. The original drug accountability records will be retained by the site.

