10.3. Treatment Compliance

The study drug is to be administered by study personnel. Administration dates and times must be recorded in the CRFs. If any portion of a dose of study drug is not administered, an explanation must be provided in the source document and on the CRF.

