1.2. Study Design

This is a Phase 2, uncontrolled, three-stage, ascending-dose-escalation study in patients with TMA: aHUS, TTP, or HSCT-TMA. As originally designed, the primary outcomes to be measured were safety and clinical activity. The secondary outcomes to be measured were PK, PD, and immunogenicity (i.e., presence of anti-drug antibody [ADA] response). Amendment [REDACTED] discontinued enrollment of patients with aHUS and TTP. Amendment [REDACTED] provides for collection of additional data from patients with HSCT-TMA, changes the primary and secondary objectives to focus on HSCT-TMA, and defines criteria by which to determine clinical response to treatment. Amendment 11 also provides for collection of PK and PD measures for analysis within integrated population PK and PD analyses across different studies.

In Stage 1 of the study, OMS721 was administered to 3 cohorts (Cohorts 1, 2, and 3), with dose escalation by cohort to identify the optimal dosing regimen. After enrollment and treatment of each cohort, there was a safety review to determine whether dose escalation should proceed. In Stage 2, the dose selected in the first stage was administered to expanded cohorts initially planned to be 40 patients per cohort with distinct etiologies (aHUS alone in 1 cohort, and TTP or HSCT-TMA in the other cohort). As of Amendment 10 of the protocol, enrollment of aHUS and TTP patients was closed.

Each patient in Stage 1 received 4 weekly doses of OMS721. Prior to Amendment 10, patients in Stage 2 with aHUS received 12 weekly doses and patients with TTP or HSCT-TMA received 4 weekly doses, and Stage 3 allowed for additional treatment based upon the patient's response to therapy. As of Amendment 11 of the protocol, Stage 1 is complete.

OMS721 will be administered by intravenous (IV) infusion. The planned enrollment is up to approximately 60 patients overall. The stages, cohorts, and treatments are provided in [Table 1](#).

Table 1: OMS721-TMA-001 Treatment Stages and Cohorts

Cohort and (Stage)	Number of Patients			OMS721 Dose
	aHUS	TTP	HSCT-TMA	
1 (Stage 1)	3	0	0	0.675 mg/kg weekly x 4
2 (Stage 1)	2	1	0	2.0 mg/kg weekly x 4
3 (Stage 1)	2	0	2	4.0 mg/kg weekly x 4
4 (aHUS only) (Stage 2 and 3)	14	0	0	4.0 mg/kg weekly x 12 for each Stage
	4	0	0	400 mg weekly x 12
5 (TTP or HSCT-TMA) (Stage 2 and 3)	0	4	22	4.0 mg/kg weekly x 4 for each Stage
5 (TTP or HSCT-TMA) (Stage 2 and 3)	0	0	4	370 mg weekly x 4 for each Stage

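### Exposure totals are planned in mL although two product strengths are involved, so the 4 mg/kg and 370 mg HSCT-TMA columns are on different scales; mg would be the better unit

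*SAP*

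**What the plan says.** SAP 3.2.2.2 (Extent of Exposure) states: "Scheduled drug administrations will be summarized with the total dose volume (mL) received, the total intended dose volume (mL"). The number of doses and the duration of treatment are summarized too, all by dose and disease, and a dosing listing is planned. No total in mg is planned.

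The section gives two rules for intended volume per administration:

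- mg/kg regimens: the mg/kg dose times the smaller of body weight and 100 kg, divided by 100.
- 370 mg regimen: 370/185 = 2 mL.

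Relative dose intensity (RDI) is total volume received as a percentage of total volume intended.

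Protocol Section 9 gives the reason for the two divisors: "Two formulations are available, the higher concentration drug product (185 mg/mL) and the lower concentration drug product (100 mg/mL"), depending on the amendment under which the patient enrolled.

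SAP 1.2, Table 1, lists 24 HSCT-TMA patients on 4 mg/kg (2 in Cohort 3, 22 in Cohort 5) and 4 on 370 mg. It also lists four aHUS patients on "400 mg weekly x 12". The protocol synopsis gives Cohort 4 only as "OMS721 Dose 4.0 mg/kg IV weekly x 12". Protocol 13.2.1 says that HSCT-TMA analyses are summarized for 4.0 mg/kg, for 370 mg and for both doses combined.

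**The concern.** A millilitre of the 185 mg/mL product holds 1.85 times the drug in a millilitre of the 100 mg/mL product. Exposure in mL therefore puts the two HSCT-TMA regimens on different scales in one table. The fixed dose replaced weight-based dosing at Amendment 10, so a reader will naturally ask which regimen delivered more drug. The mL rows can give the wrong answer.

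There is also a smaller gap. The first intended-volume rule is limited to mg/kg doses and the second to 370 mg, so neither covers the 400 mg aHUS regimen.

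What is at stake is how the exposure table reads. Safety is a co-primary endpoint, and exposure is the background against which the safety tables are read. No efficacy or safety estimate is computed from these volumes.

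**Working it through.** **Inputs**

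- Divisor 100 for mg/kg doses, weight cap of 100 kg, and 370 mg at 185 mg/mL: SAP 3.2.2.2. The SAP does not label the divisor as a concentration, but dividing mg by 100 gives mL only for a 100 mg/mL product.
- Patient counts and regimens: SAP 1.2, Table 1.
- Body weight: not given in either document. I assume 70 kg and show 40 to 100 kg.
- Four doses for each regimen, the Stage 2 course.

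**The plan's own figure.** 370 mg ÷ 185 mg/mL = 2.0 mL per dose, as the SAP states. Over four doses this is 8.0 mL and 1480 mg.

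**Ratio of 4 mg/kg to 370 mg at weight w (up to 100 kg)**

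- By volume: (4w/100) ÷ 2 = 0.02w.
- By mass: 4w/370.
- Volume ratio ÷ mass ratio = 0.02w × 370/(4w) = 1.85 at every weight.
- Volumes are equal at 4w/100 = 2, so w = 50 kg. Masses are equal at 4w = 370, so w = 92.5 kg. Between these weights the 4 mg/kg regimen has more mL but fewer mg.

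| Weight (kg) | 4 mg/kg × 4: mL | 4 mg/kg × 4: mg | mL ratio to 370 mg | mg ratio to 370 mg |
|---|---|---|---|---|
| 40 | 6.4 | 640 | 0.80 | 0.43 |
| 50 | 8.0 | 800 | 1.00 | 0.54 |
| 60 | 9.6 | 960 | 1.20 | 0.65 |
| 70 | 11.2 | 1120 | 1.40 | 0.76 |
| 80 | 12.8 | 1280 | 1.60 | 0.86 |
| 90 | 14.4 | 1440 | 1.80 | 0.97 |
| 100 or more (capped) | 16.0 | 1600 | 2.00 | 1.08 |

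At 70 kg the 4 mg/kg regimen looks 40% larger in mL and is 24% smaller in mg.

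**A combined HSCT-TMA column.** With 24 patients on 4 mg/kg at 70 kg and 4 on 370 mg, all given four doses:

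- Mean volume: (24 × 11.2 + 4 × 8.0)/28 = 10.74 mL.
- Mean mass: (24 × 1120 + 4 × 1480)/28 = 1171 mg.
- Converting 10.74 mL back gives 1074 mg at 100 mg/mL or 1987 mg at 185 mg/mL. Neither is 1171 mg.

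**RDI.** If the product given has the concentration assumed for the regimen, volume received ÷ volume intended equals mg received ÷ mg intended, because the concentration cancels.

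**The 400 mg regimen.** 400/100 = 4.00 mL or 400/185 = 2.16 mL per dose; over 12 doses, 48.0 or 25.9 mL. In mg it is 400 per dose and 4800 over 12 doses, whatever the concentration.

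**The case against.** The exposure tables are split by dose, and no comparison of mL across regimens is planned. Within a regimen, mL becomes mg by one multiplication: 100 for mg/kg columns and 185 for 370 mg. RDI has no unit, and dose counts, duration and a listing are planned as well. Neither exposure section names a combined column. The reversal of order depends on weights that the documents do not give. All of this stands, and it is why the point is small. The factor of 1.85 needs no assumed weight, however, and the one-step conversion does not rescue a combined column.

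Three stronger readings are tempting, and the documents do not support them.

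- *RDI is wrong for the 4 mg/kg patients.* It would read about 54% (100/185) for a full dose drawn from the 185 mg/mL product. Protocol 9.1.3 says "As of Amendment 10 of this protocol, only the Drug Product, OMS721 185 mg/mL formulation will be used", and the notes to Protocol Table 1 keep patients in mid-treatment on their original dose, so this is possible. Section 9 ties product to the amendment at enrollment, however, and 9.1 says only that "the 100 mg/mL formulation will not be used for newly enrolled patients". It may have affected no one.
- *The 400 mg patients will show a badly wrong RDI.* A fully dosed patient would show 54% or 185% only if the programmer chose the concentration that was not used. The documents point to 4.0 mL at 100 mg/mL: aHUS enrollment closed at Amendment 10, 400 mg is exactly two of the 2 mL, 100 mg/mL vials, and it equals the capped dose of the existing rule (4 × 100). This is missing detail that an analyst would most likely fill correctly. Because protocol text is blacked out, the protocol's silence on 400 mg proves little.
- *Efficacy or safety results are affected.* They are not. Even the per-protocol set is defined by days of treatment, not by volume.

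**Conclusion.** The point holds as a cheap improvement. On the SAP's own rules, the mL totals for the two HSCT-TMA regimens differ in scale by a factor of 1.85. At an assumed 70 kg over four doses, they order the regimens opposite to the drug given (11.2 against 8.0 mL; 1120 against 1480 mg). The factor assumes that each regimen was drawn from the product strength that the SAP assigns to it. The reversal further assumes equal numbers of doses and a weight between 50 and 92.5 kg. A combined column, if produced under Protocol 13.2.1, would have no dose meaning.

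RDI is sound within a regimen when product and assumed concentration agree. The 400 mg gap would not justify a change by itself, but the same remedy closes it.

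**What to change.** Report dose received, dose intended and RDI in mg.

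- Intended mg per administration: mg/kg dose × min(weight, 100 kg) for the weight-based regimens; 370 mg or 400 mg for the fixed regimens.
- Received mg: volume given × concentration of the product given.
- Where the product cannot be linked to a dose, use the concentration assigned to the regimen and flag the dose in the listing.

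This is right whether or not product strength always followed regimen. Protocol 13.2.7 already plans the anti-drug antibody summary by dose and also by formulation, so the two need not coincide.

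The cost is one SAP formula, its programming and possibly a data link. Product identity is required in the accountability records (Protocol 9.1.5: "The documentation should include the identification of the Drug Product used"). Protocol 10.3 says "Administration dates and times must be recorded in the CRFs" and does not mention product.

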3.2.3. Demographics and Baseline Characteristics

Demographic and other baseline characteristics will be listed and summarized by dose and disease for the safety population. Baseline characteristics include

- Weight (kg)
- Body mass index (BMI)
- Baseline platelet count
- Baseline platelet count ($< 20,000$ or $\geq 20,000$ platelets/ μL , HSCT-TMA only)
- Baseline LDH
- Baseline Hgb
- Baseline creatinine
- Baseline haptoglobin

3.2.4. Thrombotic Microangiopathy History

TMA history will be summarized with descriptive statistics by dose and disease for the safety population:

- Time (months or years) from TMA diagnosis to Day 1
- Time from HSCT to TMA diagnosis (HSCT-TMA only)
- Total number of previous episodes of TMA
- Time (days or months) from the onset of the current TMA episode to Day 1
- Shiga-toxin producing *E. Coli* test for current TMA episode (positive or negative for a-HUS patients only)
- Direct coombs test for current TMA episode (positive or negative)
- Most recent ADAMTS13 test result prior to dosing (historical data is allowed)
- Any transfusions within the 2 weeks prior to or on the first OMS721 dose date (Yes or No, HSCT-TMA only)
- Other risk factors for the HSCT-TMA patients will be identified after review of their historical data.

3.2.5. Hematopoietic Stem Cell Transplant-Associated Thrombotic Microangiopathy History

HSCT history will be summarized with descriptive statistics by dose for the safety population:

- Underlying disease
- Donor source (related or unrelated)
- Time from HSCT to Day 1
- Graft-versus-host disease (Yes or No)
- Significant infection (Yes or No)
- Refractory primary disease or primary disease relapse (Yes or No)
- Graft failure or non-engraftment (Yes or No)
- Female-to-male transplant (Yes or No)
- Multiple organ TMA involvement (Yes or No)
- Mismatched donor (Yes or No)
- Neurological findings at baseline (Yes or No)
- Renal dysfunction at baseline (Creatinine > ULN, or spot urine protein $\geq 2+$ or > 30 mg/dL; Yes or No)

3.2.6. Prior and Concomitant Medications

Concomitant medications will be coded with World Health Organization Drug Dictionary. Prior (medications with end dates prior to the first dose date) and concomitant medications will be listed.

Conservative treatments and their durations prior to the first dose of OMS721 will be listed for the HSCT-TMA patients in the safety population.

3.2.7. Medical and Surgical History

A listing of reported medical and surgical history will be provided.

3.3. Analysis of Pharmacokinetic, Pharmacodynamic, and Immunogenicity Endpoints

See Section [2.8.3](#).

3.4. Analysis of Safety Endpoints

3.4.1. Clinical Adverse Events

Adverse events collected during the study and significant AEs will be combined for analysis. They will be labeled as adverse events for simplicity. Significant AEs are the AEs that occurred outside the protocol-specified reporting period and will be collected for the HSCT-TMA patients only. For reporting purposes, AEs will be divided into 2 categories:

1. Those that occurred prior to the start of study treatment (pre-treatment events) and
2. Those that occur or worsen in intensity after the start of study treatment (treatment-emergent adverse events).

Summary of AEs will include the non-serious AEs during the AE evaluation period and all reported serious AEs. The AE evaluation period is defined from the time of informed consent to 37 days after the last study drug administration.

All AEs will be classified by system organ class and preferred term using the Medical Dictionary for Regulatory Activities (MedDRA). An AE is considered treatment related if the relationship to study drug is either probable or possible as assessed by the investigator.

Patient incidence of the following AEs will be provided:

- Pre-treatment AEs by MedDRA System Organ Class (SOC), preferred term, dose and disease
- Treatment-emergent AEs by MedDRA SOC, preferred term, dose and disease
- Treatment-emergent AEs by MedDRA preferred term, dose and disease
- Treatment-related AEs by MedDRA SOC, preferred term, dose and disease
- Treatment-emergent AEs by MedDRA preferred term, maximum severity, dose and disease
- AEs leading to study discontinuation by MedDRA SOC, preferred term, dose and disease
- Treatment-emergent serious AEs (SAEs) by MedDRA SOC, preferred term, dose and disease
- Treatment-related SAEs by MedDRA SOC, preferred term, dose and disease
- AEs leading to death by MedDRA SOC, preferred term, dose and disease

In addition, the following analyses will be performed:

- Treatment-emergent AEs and treatment-emergent SAEs during the AE evaluation period will be summarized separately for patients with and without anti-drug antibody postdose.
- Treatment-emergent AEs that started or worsen in intensity after the AE evaluation period will be summarized with patient incidence by SOC, preferred term, disease group and dose level.
- Pre-treatment and treatment-emergent significant infections will be summarized by infection type which will be determined before database lock and will be documented in the CSR.

Listings of all AEs collected will be provided.

